5.7 Prior and Concomitant Medication

World Health Organization Drug Dictionary (WHO-DRUG) 2013SEP01 (or newer) and the Anatomical Therapeutic Chemical (ATC) classification system will be used to classify prior and concomitant medications by therapeutic class.

Prior medication is defined as any medication with the start date prior to the date of the first dose of investigational product. Prior treatment given for the subject's UC was recorded for the year prior to the Screening Visit, where available. All other prior treatment, including but not limited to herbal treatments and vitamins, received within 21 days of the date of first dose of investigational product was recorded.

Concomitant medication is defined as any medication with a start date prior to the date of the first dose of investigational product and continuing after the first dose of investigational product or with a start date between the dates of the first dose of investigational product and the end of the follow-up period, inclusive. Any medication with a start date after the date of the end of the follow-up period will not be considered a concomitant medication.

Both prior and concomitant medication usage will be summarized by the number and proportion of subjects receiving each medication within each therapeutic class and preferred term.

Medications can be counted both as prior and concomitant medication. Multiple medication usage by a subject in the same category will be counted only once.

Separate summaries for both prior and concomitant medication usage will be produced for both the Double-blind Acute and Double-blind Maintenance Phase Safety Analysis Sets by treatment arm and overall. For the Overall Safety Analysis Set, summaries for both prior and concomitant medication usage will be presented overall only. For the Open-label Acute Phase Safety Set, summaries for concomitant medication usage will be presented by high-dose.

All prior and concomitant medication will be listed.

5.8 Analysis of Efficacy

All efficacy analyses will be based on the Safety Analysis Set specific to the study phase. Baseline is defined as the last observation prior to first dose of investigational product in the study. The Double-blind Acute Phase Week 8/Withdrawal visit (Visit 3.2) is treated as the Open-label Acute Phase Week 0 for subjects continuing into the Open-label Acute Phase from this visit. The Double-blind Acute Phase Week 8/Withdrawal visit (Visit 3.2) is treated as the Double-blind Maintenance Phase Week 0 for subjects continuing into the Double-blind Maintenance Phase from this visit. The Open-label Acute Phase Week 8/Withdrawal visit (Visit 4.2) is treated as the Double-blind Maintenance Phase Week 0 for subjects continuing into the Double-blind Maintenance Phase from this visit. For subjects who enter the Double-blind Maintenance Phase directly, the Baseline Visit (Visit 2) is treated as the Double-blind Maintenance Phase Week 0.

The final on treatment assessment (FoTA) for the Double-blind Acute phase is defined as data from the Double-blind Acute phase Week 8, or early withdrawal visit if subject withdrew prior to Week 8. The FoTA for the Open-label Acute phase is defined as data from the Open-label Acute phase Week 8, or early withdrawal visit if subject withdrew prior to Week 8. The FoTA for the Double-blind Maintenance phase is defined as data from the Double-blind Maintenance phase Week 26, or early withdrawal visit if subject withdrew prior to Week 26.

Details of the derivation of the composite endpoints (partial and full UC-DAI scores) are included in Section 8.2.

5.8.1 Primary Efficacy Endpoints and Analysis

The primary endpoints for this study are defined separately for both the Double-blind Acute Phase and Double-blind Maintenance Phases and will be conducted using the appropriate Safety Analysis Set for the phase:

5.8.1.1 Double-blind Acute Phase

The primary efficacy endpoint for the Double-blind Acute Phase is defined as the proportion of subjects with a clinical response (defined as partial UC-DAI \leq 1 with rectal bleeding=0, stool frequency \leq 1, and PGA=0) at Week 8.

- Subjects with missing data at Week 8 will be assumed not to have had a clinical response. The primary efficacy endpoint will be compared between treatment arms using a continuity corrected chi-squared test on the Double-blind Acute Phase Safety Analysis Set. If any of the expected cell counts are very low (i.e., less than 5), then Fisher's Exact Test will be used as an alternative analysis method.
- The null hypothesis to be tested is that there is no difference in the proportion of subjects with a clinical response at Week 8 between low and high doses of MMX mesalamine/mesalazine.
- The number (n, %) of subjects with a clinical response at Week 8 and the difference between treatment arms, together with the 95% CI (2-sided), and associated p-value will be presented. The odds ratio comparing the two treatments, together with the 95% CI (2-sided) will also be presented.

5.8.1.2 Double-blind Maintenance Phase

The primary efficacy endpoint for the Double-blind Maintenance Phase is defined as the proportion of subjects who have maintained a clinical response (defined as partial UC-DAI \leq 1 with rectal bleeding=0 and stool frequency \leq 1 and PGA=0) at Week 26.

- Subjects with missing data at Week 26 will be assumed not to have had a clinical response. The primary efficacy endpoint will be compared between treatment arms using a Cochran-Mantel-Haenszel (CMH) test stratifying for 3 levels of Week 8 responder status (entered Maintenance Phase directly, responder at Week 8 of the Double-blind Acute Phase, or responder at Week 8 of the Open-label Acute Phase) on the Double-blind Maintenance Phase Safety Analysis Set.

- The null hypothesis to be tested is that there is no difference in the proportion of subjects with a clinical response at Week 26 between low and high doses of MMX mesalamine/mesalazine.
- The number (n, %) of subjects with a clinical response at Week 26 and the difference between treatment arms, together with the 95% CI (2-sided), and associated p-value will be presented. The odds ratio comparing the two treatments, together with the 95% CI (2-sided) will also be presented.

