Table 3: Double-blind Maintenance Phase

Visit	1 (Screening) ^a	Recommended Telephone call ^b	2 (Baseline) ^a	5	5.1	5.2	6 ^c
Day/Month^d	Day -21 to -3	Day -7 to -4	Week 0	Weeks 2-4	Week 13	Week 26/ Withdrawal	Follow-up
Review DUCS instructions, ability to read and understand e-diary with subject/caregiver	✓						
Subject/caregiver e-diary entry: rectal bleeding, stool frequency, DUCS _h and Overall Current Health ^h	✓		✓		✓	✓	
Assessment of e-diary compliance ^a		✓					
Global Change in Health ⁱ						✓	
IMPACT III ⁱ			✓			✓	
PUCAI (where applicable)			✓			✓	
Average stool frequency ^{j, k, l}			✓		✓	✓	
Average rectal bleeding ^{j, k, l}			✓		✓	✓	
PGA ^{k, l}			✓			✓	
Endoscopy (flexible sigmoidoscopy or colonoscopy) for study eligibility ^{d, l, m}	✓		✓				
Endoscopy (flexible sigmoidoscopy or colonoscopy), where possible ^j						✓	
IRT entry	✓		✓	✓	✓	✓	
Calculate partial UC-DAI			✓			✓	
Investigational product dispensed			✓	✓	✓		
Investigational product collected and compliance calculated				✓	✓	✓	
Adverse events	✓	✓	✓	✓	✓	✓	✓
Concomitant medication	✓		✓		✓	✓	✓

Table 3: Double-blind Maintenance Phase

Visit	1 (Screening) ^a	Recommended Telephone call ^b	2 (Baseline) ^a	5	5.1	5.2	6 ^c
Day/Month ^d	Day -21 to -3	Day -7 to -4	Week 0	Weeks 2-4	Week 13	Week 26/ Withdrawal	Follow-up

Abbreviations: DUCS=Daily Ulcerative Colitis Scale for children and caregivers; eCRF=electronic case report form; e-diary=electronic diary; IRT=interactive response technology; PGA=Physician's Global Assessment; PUCAI=Pediatric Ulcerative Colitis Activity Index; UC-DAI=Ulcerative Colitis Disease Activity Index.

^a The Screening Visit (Visit 1) and the Baseline Visit (Visit 2) in Table 3 apply only to subjects entering directly into the Double-blind Maintenance Phase.

^b Approximately 4 to 7 days prior to the Baseline Visit (Visit 2) and prior to each subsequent visit (Visits 5, 5.1, and 5.2), it is recommended that site staff telephone the subject or the subject's caregiver to remind them to enter UC-DAI symptoms (rectal bleeding and stool frequency) into the e-diary every night, even if the subject has no symptoms.

^c Follow-up assessment may be performed via telephone call within 7 days of the last dose of investigational product.

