5.3 Prohibited Treatment

[Table 5](#) details the common prior treatments that are excluded medications for this study.

Table 5: Common Prior Excluded Treatments

Treatment	Minimum Time Before Screening					
	3 days	7 days	21 days	4 weeks	6 weeks	No Use Permitted
Anti-diarrheals and/or anti-spasmodics ^a	X					
Antibiotics ^a		X				
Anti-inflammatory drugs ^{a, b, c}		X				
Vaccination/immunization			X			
Systemic or rectal corticosteroids				X		
Immunomodulators					X	
Oral anticoagulants ^b						X
Biologics						1 year

^aNon-steroidal anti-inflammatory drugs, anti-diarrheals, laxatives, and antibiotics are permitted for up to 10 consecutive days if taken for a condition unrelated to UC

^bSee Section 4.2 (Exclusion Criteria) for exceptions to these excluded prior medications.

^cDoes not include current 5-aminosalicylic acid treatment

Administration of the following medication during the study is not permitted and will result in withdrawal of the subject:

- Systemic or rectal corticosteroids.
- Other medications containing 5-ASA (eg, sulfasalazine or mesalamine/mesalazine), including topical administration
- Immunomodulators (eg, 6-mercaptopurine, azathioprine, cyclosporine, methotrexate)
- Biologics (eg, anti-tumor necrosis factor agents, such as infliximab).

The following are also prohibited: nicotine patches, any products containing fish oils (fish oils are prohibited unless on a stable dose 4 weeks prior to the Screening Visit [Visit 1] and throughout study participation), or any investigational or marketed drug that may interfere with the evaluation of the investigational product.

In the event of any prohibited UC medication use during the Double-blind Maintenance Phase, the subject should notify the investigator who will assess if the subject is experiencing a possible acute flare.

Non-steroidal anti-inflammatory drugs, anti-diarrheals, laxatives, antibiotics, and drugs that cause constipation are permitted for up to 10 consecutive days if taken for a condition unrelated to UC. Prophylactic use of a stable dose of aspirin up to 325mg/day for cardiac disease is permitted. For mild, acute pain, acetaminophen is recommended.

Administration of seasonal vaccines is permitted during the study; however, routine vaccinations should be deferred until after study completion where possible.

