7.1.5 Follow-up Period (Visit 6)

The follow-up period for this protocol is 7 days following last dose of investigational product. All subjects, whether they have completed the study or withdrawn early, must have a follow-up contact.

At the end of this period there will be a visit or telephone call initiated by the site staff to query for SAEs, AEs, and concomitant treatments. All AEs and SAEs that are not resolved at the time of this contact will be followed to closure (see Section [8](#)).

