7.2 Handling of Dropouts or Missing Data

For the primary analysis of the primary efficacy endpoint, subjects with missing data at Week 8 or Week 26 for the Double-blind Acute Phase or Double-blind Maintenance Phase, respectively, will be assumed not to have had a clinical response and will be considered treatment failures.

Sensitivity analyses to examine the handling of missing data for the primary efficacy endpoint include complete-case analysis and last observation carried forward. These are described in Section 7.7.

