8.2 Derived Efficacy Endpoints

- Stool frequency and rectal bleeding score:
 - For both stool frequency and rectal bleeding, the symptom score (collected via the electronic diary [e-diary]) is defined as the average of the scores from the last available 3 days from the 5 days immediately prior to the visit (days -1 to -5). If there are fewer than 3 days of data available during days -1 to -5, the average will be calculated from any available days within the period. If there are no available days during the period, then the symptom score will be missing for that visit. Data collected on days when bowel preparations have been administered or when endoscopy has been performed will be excluded.
 - For stool frequency and rectal bleeding, the symptom score will be grouped into a category (0, >0 - <1, 1 - <2, 2 - <3, and 3).
- Partial UC-DAI score:
 - Sum of rectal bleeding score, stool frequency score and PGA score
- Full UC-DAI score:
 - Sum of rectal bleeding score, stool frequency score, PGA score and endoscopy score
- Clinical response: partial UC-DAI ≤ 1 (rectal bleeding=0 and stool frequency ≤ 1 and PGA=0)
- Clinical and endoscopic response: UC-DAI ≤ 2 with rectal bleeding=0 and stool frequency ≤ 1 and PGA=0, and mucosal healing (endoscopy score ≤ 1) based on central reading
- Week 8 responder status is defined based on clinical response: entered Maintenance Phase directly, responder at Week 8 of the Double-blind Acute Phase, or responder at Week 8 of the Open-label Acute Phase.

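### Prohibited UC medication first identified at the Week 8 or Week 26 visit, or at Maintenance follow-up, can leave a child counted as a responder, because only missing data makes a failure

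*SAP*

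**What the plan says.** **Response.** SAP 8.2 builds the partial UC-DAI as "Sum of rectal bleeding score, stool frequency score and PGA score" and derives clinical response from those components. Medication plays no part.

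**Failure.** SAP 5.8.1.1 says "Subjects with missing data at Week 8 will be assumed not to have had a clinical response", and SAP 5.8.1.2 says "Subjects with missing data at Week 26 will be assumed not to have had a clinical response". SAP 7.2 repeats that children with missing endpoint data "will be assumed not to have had a clinical response and will be considered treatment failures". No other event makes a child a failure.

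**Prohibited drugs.** For the four classes (systemic or rectal corticosteroids, other 5-ASA products, immunomodulators, biologics), Protocol 5.3 says: "Administration of the following medication during the study is not permitted and will result in withdrawal of the subject". It sets no dose, duration or indication threshold. For the Maintenance Phase it adds that "the subject should notify the investigator who will assess if the subject is experiencing a possible acute flare".

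**When medication is asked about.** In Protocol Table 3 the row "Concomitant medication" is ticked after Week 0 only at Weeks 13 and 26 and at follow-up, and not at the Weeks 2-4 visit. At follow-up, under Protocol 7.1.5, "there will be a visit or telephone call initiated by the site staff to query for SAEs, AEs, and concomitant treatments". In the Acute Phase (Table 1) it is ticked at Weeks 2, 4 and 8, and follow-up applies only to children leaving the study.

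**The concern.** The same event can lead to opposite outcomes depending only on when the site learns of it. Use found in mid-phase leads to withdrawal and a missing endpoint, so the child is a failure. Use found at or after the endpoint visit comes when the scores exist, and nothing in the SAP overrides them. A child whose disease was controlled by another active drug would then be credited to the assigned MMX dose.

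The stated product of this study is an estimate of response at each dose, and these cases can only raise an arm's rate. The sponsor has already treated this kind of confounding as important: Amendment 5 withdrew permission for rectal steroids during the study for that reason.

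**Working it through.** The plan gives no figure on this point to reproduce. The check traces the rules and then sizes one affected child.

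**1. Three children in Maintenance who took the same prohibited drug, all well at their last assessment**

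| Use identified | Protocol 5.3 | Week 26 scores | Primary result |
|---|---|---|---|
| Week 13 | withdrawn | missing | non-responder |
| Week 26 visit | too late to prevent scoring | present | responder |
| Follow-up contact | too late to prevent scoring | present | responder |

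The first row is an inference. Visits 3.2 and 5.2 are labelled as both the endpoint and the withdrawal visit, and the SAP gives no visit window. However, the final on-treatment assessment (SAP 5.8) and the complete-case analysis (SAP 7.7.1) both separate an early withdrawal from Week 8 or Week 26. If early withdrawal scores were instead mapped to the endpoint, users found early could also be responders and the gap would be wider.

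**2. Does anything else remove the late-identified child?**
- Analysis sets: all efficacy analyses use the Safety Analysis Sets, and there is no per-protocol set (SAP 5.2).
- Deviations and medications are classified, summarized and listed, but not linked to response (SAP 5.4, 5.7).
- The complete-case analysis drops early withdrawals only, so this child stays in as a completer (SAP 7.7.1).
- The factors listed for scoring PGA (Protocol 7.2.1.1) do not include medication use.

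**3. Window first asked about at the endpoint visit**
- Maintenance: 26 − 13 = 13 weeks.
- Acute: 8 − 4 = 4 weeks.

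**4. Size per child**

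Inputs: at least 80 children in Maintenance and 53 in the Acute Phase (SAP 3.5), allocated 1:1 (SAP 3.3), so 40 per arm and 26 or 27 per arm. The SAP attaches its two-sided 95% interval to the difference between arms (5.8.1.1, 5.8.1.2). It gives no interval method or expected response rate, so an unstratified Wald interval and a 50% rate in both arms are assumed.

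- Shift in an arm's rate: 1/40 = 2.5 points; 1/26 = 3.85 and 1/27 = 3.70 points.
- Half-width for the difference, 1.96 × √[p(1−p)(1/n₁ + 1/n₂)]:
  - Maintenance: 1.96 × √[0.25 × (1/40 + 1/40)] = 21.9 points.
  - Acute: 1.96 × √[0.25 × (1/26 + 1/27)] = 26.9 points.
- One child as a share of the half-width: 2.5/21.9 = 11%; 3.85/26.9 = 14%.
- At assumed rates of 30% or 70% the half-widths are 20.1 and 24.7 points, and the shares are 2.5/20.1 = 12% and 3.77/24.7 = 15% (taking 1/26.5 = 3.77 points).

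**5. Direction for the dose comparison (all counts assumed)**

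Take 40 per arm, with 20 low-dose and 24 high-dose responders among children with no prohibited use: 60.0 − 50.0 = 10.0 points if every user is a failure. If four low-dose users and one high-dose user are found late and count as responders, the difference is 25/40 − 24/40 = 2.5 points. With one low-dose and four high-dose users it is 28/40 − 21/40 = 17.5 points. With two in each arm it stays at 10.0. The effect on the difference can therefore go either way.

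**The case against.** The strongest reply is that few children can reach this position. Families are told to report prohibited use in Maintenance (Protocol 5.3). Unscheduled flare visits (7.2.1.1), recording of worsening as an adverse event (8.1.4), and adverse-event checks at Visit 5 and by telephone may also bring use to light. Use first found at follow-up must also have been missed at the Week 26 visit. Known users are withdrawn, medications and deviations are tabulated by arm, and this is an estimation study without formal testing.

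Most of this stands, and it limits the likely size. It does not close the gap, because the self-report and adverse-event routes depend on what families volunteer. The tables would show the use without changing the response rate.

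A reader might infer more than the documents support:
- **That prohibited use is ignored altogether.** It is not: users found early are withdrawn and, on the natural reading, are primary failures.
- **That response rates are in fact inflated, or one dose favoured.** No document reports such a case, and the direction for the difference is unknown.
- **That the LOCF analysis has a separate defect.** A withdrawn user who was well at the withdrawal visit can be a LOCF responder. But carrying forward the last status is what LOCF does, and it is a sensitivity analysis set beside a primary analysis that counts that child as a failure.
- **That the Acute Phase is equally exposed.** Its unasked window is 4 weeks, and its follow-up contact covers only children leaving the study.

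**Conclusion.** The point holds for prohibited use first identified at the Week 8 or Week 26 visit or, in Maintenance, at follow-up. As written, the scoring rule would credit another drug's effect to the assigned dose for such a child, and no planned analysis corrects it.

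The effect is modest unless several users fall in one arm. It rests on the assumed 50% response rate, on equal arms at the planned sizes, and on reading early withdrawal as missing endpoint data. The change is worth making because it is cheap and prevents a choice after unblinding. It does not call the design into question.

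**What to change.** Add to SAP 8.2, and apply in 5.8.1.1, 5.8.1.2, 7.2 and the binary secondary responder endpoints:

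> A subject who took any medication that requires withdrawal under Protocol 5.3 (systemic or rectal corticosteroid, other 5-ASA, immunomodulator, biologic) after the first dose of the phase and before the Week 8 or Week 26 assessment is a non-responder, whatever the scores and whenever the use is identified.

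- Set no dose, duration or indication threshold. Protocol 5.3 has none, and any exemption would restore the dependence on discovery time for the exempted cases.
- Do not count apparent use, in any class, that arises only from an imputed date under SAP 8.6. A stop date with day and month missing, in the same year as the last dose, is set to the last-dose date (8.6.2). A drug stopped before entry could therefore appear to span the whole phase. UC treatment is recorded for the year before Screening (Protocol 5.1), so such records are plausible.
- Identify cases by blinded medication review before unblinding.
- Keep the as-scored analysis as a sensitivity analysis, and show separately there any rectal steroid use that was permitted under Amendment 4.
- Apply the same rule in the LOCF analysis for consistency.

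The cost is SAP wording and one blinded review of data already collected. Response rates may be slightly lower, and a child given a short steroid course for another illness will count as a failure, as already follows when Protocol 5.3 withdrawal leaves the endpoint missing.

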5.8.2 Secondary Efficacy Endpoints and Analysis

The secondary endpoints for this study are defined separately for both the Double-blind Acute and Double-blind Maintenance Phases and will be conducted using the appropriate Safety Analysis Set for the phase.

5.8.2.1 Double-blind Acute Phase

- The proportion of subjects with a clinical and endoscopic response at Week 8, defined as UC-DAI ≤ 2 with rectal bleeding=0 and stool frequency ≤ 1 and PGA=0, and with mucosal healing (endoscopy score ≤ 1) based on central reading. In addition, there must be at least a 1-point reduction in endoscopy score from baseline. This endpoint will be compared between treatment arms using a continuity corrected chi-squared test. If any of the expected cell counts are very low (i.e., less than 5), then Fisher's Exact Test will be used as an alternative analysis method. Subjects with missing data at Week 8 will be assumed not to have had a clinical response. Subjects who completed week 8 but who did not have central reading endoscopies at both baseline and week 8 will be excluded.
- The proportion of subjects with a clinical and endoscopic response at Week 8, defined as UC-DAI ≤ 2 with rectal bleeding=0 and stool frequency ≤ 1 and PGA=0, and with mucosal healing (endoscopy score ≤ 1) based on local reading. In addition, there must be at least a 1-point reduction in endoscopy score from baseline. This endpoint will be compared between treatment arms using a continuity corrected chi-squared test. If any of the expected cell counts are very low (i.e., less than 5), then Fisher's Exact Test will be used as an alternative analysis method. Subjects with missing data at Week 8 will be assumed to be treatment failures. Subjects with missing data at Week 8 will be assumed not to have had a clinical response. Subjects who completed week 8 but who did not have local reading endoscopies at both baseline and week 8 will be excluded.
- The change in the DUCS score from baseline to Week 8 of the Double-blind Acute Phase. This endpoint will be compared between treatment arms using an analysis of covariance (ANCOVA), including treatment arm as a factor and the baseline DUCS score as a covariate in the model.
- The percentage of subjects with an improvement (change of ≥ 20 points) in PUCAI score from baseline to Week 8 of the Double-blind Acute Phase. This endpoint will be compared between treatment arms using a continuity corrected chi-squared test. If any of the expected cell counts are very low (i.e., less than 5), then Fisher's Exact Test will be used as an alternative analysis method. Subjects with missing data at Week 8 will be assumed not to have had a clinical response.

